13.2.3.2 Analysis of Secondary Endpoint Variables

13.2.3.2.1 Key Secondary Variables of Diabetes Status

The following key secondary efficacy endpoint variables will be analysed with the same model (MMRM) as the primary efficacy endpoint:

- Change in IDAA1c between baseline and 15 months.
- Change in HbA1c between baseline and 15 months.
- Change in daily exogenous insulin consumption between baseline and 15 months.

The analysis of key secondary endpoints will be subject to the same sensitivity analyses as the primary efficacy analysis. However, exploration of key secondary endpoints by covariate and subgroups analyses will be based on the observed results for respective endpoint.

13.2.3.2.2 Other Secondary Variables of Diabetes Status

Summary statistics (including Student's t based 95% CIs and p-value for the difference between Diamyd and Placebo) for change in glycemic variability/fluctuations (evaluated from data from continuous glucose monitoring FreeStyle LibrePro, FGM) over 14-day period between Screening and 15 months. Further analysis of the data from the 14-day FreeStyle LibrePro, periods will be presented in the SAP.

The following secondary efficacy endpoint variables will be analyzed with the same model as the primary efficacy endpoint (details on log-transformations will be given in the SAP):

- Proportion of patients with by IDAA1c ≤ 9 at 15 months.
- Change in Fasting C-peptide between baseline and 15 months.
- Change in C-peptide measured at 30, 60, 90, and 120 minutes during MMTT at 15 months.
- Change in maximum C-peptide during MMTT between baseline and 15 months.

The following secondary efficacy endpoints will be presented using summary statistics and p-value from Cochran/Mantel-Haenszel Test stratified for randomization strata (GAD65A level) will be given along with 95% CIs calculated according to the Clopper-Pearson method:

- Proportion of patients with a stimulated maximum C-peptide level above 0.2 nmol/L (0.6 ng/ml) at 15 months.
- Proportion of patients with a stimulated 90min C-peptide level above 0.2 nmol/L (0.6 ng/ml) at 15 months.
- Number of patients having at least 1 severe hypoglycemic event using Cochran/Mantel-Haenszel Test stratified for randomization strata (GAD65A level).
- Change in body weight and BMI between baseline and 15 months

In addition, the number of self-reported episodes of severe Hypoglycaemia (severe Hypoglycaemia defined as needing help from others and/or seizures and/or unconscious) between baseline and 15 months will be assessed using Poisson regression including randomization strata (GAD65A level) where rate ratios with 95% CI and p-value will be given.

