
Endpoints:
 
Primary Endpoint:
 
 Change in C-peptide (Area Under the Curve [AUC]_{mean 0-120 min}) during a Mixed Meal Tolerance Test (MMTT) between baseline to 15 months. 
Key Secondary Endpoints:
 
 Change in insulin-dose-adjusted HbA1c (IDAA1c) between baseline and 15 months Change in Hemoglobin A1c (HbA1c) between baseline and 15 months Change in daily exogenous insulin consumption between baseline and 15 months. 
Secondary endpoints:
 
 Other variables that indicate Diabetes Status such as plasma C-peptide, variability of blood sugar, and number of self-reported hypoglycemia. Variables that indicate treatment safety such as occurrence of adverse events (AEs), physical examinations, hematology, urine analysis, injection site reactions, GAD65A titer, vital signs and clinical chemistry. Variables that indicate effects on the immune system such as serum autoantibodies (and isotypes) to GAD65, serum cytokine levels, secretion of cytokines by immune cells in response to GAD65-stimulation, and proportions of immune cells in blood. Measurements of patient QoL by questionnaire. 
Exploratory Endpoints:
 
 All data collected at the 24-month follow-up visit will be regarded as exploratory endpoints. 
Sample size:
 
A total sample size of 106 patients is planned for a 1:1 randomization in order to provide 90% power to detect a 50% difference in geometric mean C-peptide (AUC_{mean 0-120 min}) at 15 months between the active arm and placebo arm using a two-sided test at the 0.05 level, with 10% loss to follow-up. This is based upon a t-test employing ln(X+1) normalizing transformation of C-peptide (AUC_{mean 0-120 min}) during an MMTT at 15 months and assumed mean and standard deviation estimates, on the transformed scale, of 0.134 and 0.20 respectively.
 
Analysis of Primary endpoint variable:
 
The mean change in log-transformed values will be analyzed using Mixed Model Repeated Measures (MMRM). The model for analysis will include fixed, categorical effects of treatment, randomization strata (GAD65A level), visit and treatment by visit interaction, as well as the continuous, fixed covariates of baseline value.
 
Analysis of Key Secondary endpoint variables:
 
Key secondary efficacy endpoint variables will be analysed with the same MMRM model as the primary efficacy endpoint.
 
Analysis of Secondary endpoint variables:
 
Continuous secondary diabetes status variables will be compared using the same MMRM model as for the primary efficacy endpoint.
		

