
Name of Sponsor/Company Diamyd Medical AB	Individual Study Table Referring to Part of Dossier in which the Individual Study or Study Table is Presented: Volume: Reference:	(For National Authority Use Only)
Name of Finished Product: DIAMYD® D-vitamin ██████████ ██████████		
Name of Active Ingredient: Recombinant Human Glutamic Acid Decarboxylase (rhGAD65) Calciferol		

Categorical secondary endpoints will be presented using summary statistics and p-value from stratified Cochran/Mantel-Haenszel Test.
 
For immunological secondary endpoints summary statistics will be accompanied with p-values from non-parametric statistical tests
 
Analysis of the QoL data obtained within the study will follow the EQ-5D-5L User guide.
		

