6.4.2 Secondary Endpoints

The key secondary endpoints to evaluate diabetic status are:

- Change in insulin-dose-adjusted HbA1c (IDAA1c) between baseline and 15 months.
- Change in HbA1c between baseline and 15 months.
- Change in daily exogenous insulin consumption between baseline and 15 months.

The other secondary endpoints to evaluate diabetic status are:

- Change in glycemic variability/fluctuations (evaluated from data from continuous glucose monitoring FreeStyle LibrePro, Flash Glucose Monitoring [FGM]) over 14 day period between Screening and 15 months.
- Proportion of patients with $IDAA1c \leq 9$ at 15 months.
- Proportion of patients with a stimulated maximum C-peptide level above 0.2 nmol/L (0.6 ng/ml) at 15 months.
- Proportion of patients with a stimulated 90min C-peptide level above 0.2 nmol/L (0.6 ng/ml) at 15 months.
- Number of self-reported episodes of severe hypoglycemia (Severe hypoglycemia defined as needing help from others and/or seizures and/or unconscious) between baseline and 15 months.
- Change in Rate of hypoglycemic events between baseline and 15 months.

- Number of patients having at least 1 severe hypoglycemic event between baseline and 15 months.
- Change in maximum C-peptide during MMTT between baseline and 15 months.
- Change in Fasting C-peptide between baseline and 15 months.
- C-peptide measured at 30, 60, 90, and 120 minutes during MMTT at 15 months.
- Change in body weight and body mass index (BMI) between baseline and 15 months

The secondary endpoints to evaluate safety are:

- Injection site reactions
- Occurrence of AEs
- Laboratory measurements (hematology and clinical chemistry)
- Urine analysis (microalbuminuria, creatinine)
- Physical examinations, including neurological assessments
- GAD65A titer
- Vital signs (blood pressure [BP])

The secondary endpoints to evaluate the influence on the immune system are:

- Concentrations of serum autoantibodies towards GAD65 and IA-2.
- Concentrations of serum autoantibody isotypes towards GAD65.
- Secretion of cytokines interleukin (IL)-1, IL-2, IL-5, IL-13, IL-10, IL-17, interferon (IFN) γ , and tumour necrosis factor (TNF) α by peripheral blood mononuclear cells (PBMCs) upon stimulation with GAD65.
- Serum concentrations of cytokines IL-1, IL-2, IL-5, IL-13, IL-10, IL-17, IFN γ , and TNF α .
- Secretion of cytokines IL-1, IL-2, IL-5, IL-13, IL-10, IL-17, IFN γ , and TNF α by PBMCs upon stimulation with anti-CD3 and anti-CD28.

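### Section 13.2.3.2.2 assigns a yes/no endpoint (IDAA1c ≤ 9) to the linear MMRM, and a continuous one (weight/BMI change) to CMH with Clopper-Pearson limits, against the protocol's own rules

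*Protocol*

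**What the plan says.** The synopsis gives a general rule by type of variable. For continuous endpoints: "Continuous secondary diabetes status variables will be compared using the same MMRM model as for the primary efficacy endpoint". For categorical endpoints: "Categorical secondary endpoints will be presented using summary statistics and p-value from stratified Cochran/Mantel-Haenszel Test".

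Section 13.2.3.2.2 then assigns methods endpoint by endpoint.

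- The first list, whose members "will be analyzed with the same model as the primary efficacy endpoint", contains "Proportion of patients with by IDAA1c ≤ 9 at 15 months" alongside changes in fasting, timed and maximum C-peptide.
- The second list gets summary statistics, a CMH p-value stratified by GAD65A level, and "95% CIs calculated according to the Clopper-Pearson method". It contains two C-peptide responder proportions, the number of patients with a severe hypoglycemic event, and "Change in body weight and BMI between baseline and 15 months".

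Section 6.4.2 opens a list with "The other secondary endpoints to evaluate diabetic status are", and that list includes "Change in body weight and body mass index (BMI) between baseline and 15 months". Weight and BMI are therefore diabetes-status endpoints, and the synopsis rule for continuous variables covers them.

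**The concern.** Each of the two bullets sits under a method meant for the other type of variable. Whoever writes the SAP meets two conflicting instructions for each endpoint and has to choose. For weight and BMI the detailed section, taken alone, specifies an interval that cannot be computed. For IDAA1c ≤ 9 it asks for LS means and a mean change from baseline for a yes/no outcome at a single visit. If the choice were left until after unblinding, it would be post hoc. At stake is the reporting of two secondary endpoints, not the trial's main conclusion.

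**Working it through.** **Side-by-side comparison**

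| Endpoint | Type | Synopsis rule | Section 13.2.3.2.2 |
|---|---|---|---|
| IDAA1c ≤ 9 at Month 15 | yes/no | stratified CMH | primary MMRM |
| Change in weight, BMI | continuous | primary MMRM | stratified CMH, Clopper-Pearson |
| Maximum and 90-minute C-peptide above 0.2 nmol/L | yes/no | stratified CMH | stratified CMH (consistent) |
| Change in fasting, timed, maximum C-peptide | continuous | primary MMRM | primary MMRM (consistent) |

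Section 13.2.3.1 defines the primary model: mean changes from baseline, a continuous baseline covariate, an unstructured covariance matrix and Kenward-Roger degrees of freedom. No logistic or other generalized version is mentioned. A slip for continuous IDAA1c is unlikely, because section 13.2.3.2.1 already assigns the change in IDAA1c to the MMRM as a key secondary endpoint.

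For weight and BMI, Clopper-Pearson limits are defined only for k events out of n (24/48 gives 0.352 to 0.648). A mean change in kg or kg/m² supplies no k. Section 13.2.5 requires baseline adjustment of change analyses, and a CMH test stratified by GAD65A level does not provide it. Section 13.2.3.3 repeats the weight/BMI analysis at Month 24.

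**Size of the effect**

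Inputs: 106 patients, 1:1 allocation and 10% loss (section 13.1) give 106 × 0.9 / 2 = 47.7, taken as 48 per arm. Then df = 94 and t = 1.9855. The protocol gives no responder rate, so the rates below are assumptions. The calculation is a Month 15 contrast without covariates, strata or other visits, so it only approximates the MMRM.

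*IDAA1c ≤ 9.* Pooled residual variance s² = [48·p1(1−p1) + 48·p2(1−p2)]/94. The interval is the difference ± t·√(2s²/48).

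- 2/48 vs 8/48: s² = 0.0913, half-width 12.2 points. The linear interval around 12.5 points is 0.3 to 24.7; Miettinen-Nurminen gives 0.2 to 26.2.
- 12/48 vs 19/48: s² = 0.2179, half-width 18.9 points. The linear interval around 14.6 points is −4.3 to 33.5; Miettinen-Nurminen gives −4.3 to 32.6.

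Exact enumeration over both binomials, where the arm-level lower limit is p1 − t·√(s²/48):

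| True rates | Coverage of the difference | Lower limit below 0% in the low-rate arm |
|---|---|---|
| 10% / 25% | 95.1% | 59% of trials |
| 25% / 40% | 95.1% | 1% |
| 40% / 55% | 95.1% | <0.01% |

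*Weight/BMI.* The MMRM would give a half-width of about t·√(2/48) = 0.405 residual SD. In cross-sectional SD units, with equal variances and baseline to Month 15 correlation ρ, multiply by √(1−ρ²) for the adjusted analysis or by √(2(1−ρ)) for the unadjusted change.

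| Assumed ρ | Adjusted | Unadjusted |
|---|---|---|
| 0.7 | 0.289 | 0.314 |
| 0.9 | 0.177 | 0.181 |
| 0.95 | 0.127 | 0.128 |

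Leaving out the baseline covariate costs little precision.

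**The case against.** The strongest reply is that nothing important changes. Both endpoints are non-key and outside the hierarchy in section 13.2.4. The linear interval for the IDAA1c difference behaves well, and the 59% figure depends on an assumed 10% responder rate. All of this is correct, and it limits the weight of the point.

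For weight and BMI, a CMH row-mean-score test can be run on a continuous variable, and section 13.2.2 supplies the usual summary statistics. A p-value and a description could therefore be produced. That narrows the unworkable part to the interval, but the interval is still missing and the baseline adjustment is still absent.

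The IDAA1c bullet is visibly garbled, so a slip for something else cannot be wholly excluded; either way it needs correcting.

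Section 13.2.3.2.2 also departs from the synopsis elsewhere: change in glycemic variability gets Student's t statistics rather than the MMRM. That is a separate departure and does not make these two assignments workable.

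Leaving the matter to the SAP does not answer it. For the first list the protocol defers only the details of log-transformation, and section 13.2 says the SAP will follow the protocol's outline. A difference interval and a missing-responder rule are ordinary SAP content; they follow from the repair and are not themselves protocol errors.

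**Conclusion.** The point holds: two assignments in section 13.2.3.2.2 are wrong as written and contradict the synopsis; the weight/BMI one also contradicts section 13.2.5. They should be corrected. The practical effect is small. For IDAA1c ≤ 9, inference on the treatment difference is nearly unchanged under the assumed rates, and arm-level limits fall below 0% often only when responders are rare. For weight and BMI, the detailed section gives no computable interval, while the synopsis rule would give one. These sizes rest on 48 patients per arm, assumed responder rates and correlations, and a contrast simpler than the full MMRM. The contradiction itself rests on no figure. Primary and key secondary inference, alpha and sample size are unaffected.

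**What to change.** Move the IDAA1c ≤ 9 proportion to the GAD65A-stratified CMH/Clopper-Pearson list. Move the weight and BMI change to the MMRM list, adjusted for baseline and GAD65A strata, reporting the LS-mean difference with its 95% interval. Treat the exploratory Month 24 repeat in section 13.2.3.3 the same way.

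Two consequences belong in the SAP:

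- Clopper-Pearson limits describe one arm at a time, so add an interval for the difference in proportions, for example stratified Miettinen-Nurminen. Apply it to the two C-peptide proportions as well, so that the list stays consistent.
- The missing-data approach in section 13.2.6 is tied to the MMRM, so state how patients without a Month 15 IDAA1c are counted. As an illustration, assume 53 randomized and 5 missing per arm, with 12/48 vs 19/48 observed. Observed cases give 14.6 points. Counting all missing as non-responders gives 12/53 vs 19/53 = 13.2 points (Miettinen-Nurminen −4.2 to 30.0). The extreme allocations give 17/53 vs 19/53 = 3.8 points and 12/53 vs 24/53 = 22.6 points.

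The cost is two moved bullets and two additions to the SAP. No new data are needed, and neither sample size nor alpha changes.

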- Proliferation of PBMCs upon stimulation with GAD65.
- Further exploratory immunological characterization.

The secondary endpoints of Quality of Life are:

- Change in QoL as measured by questionnaire EQ-5D-5L between baseline and Month 15.
- Quality adjusted life years (QALYs) based on the EQ-5D-5L questionnaire.

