13 STATISTICAL METHODS

13.1 Estimation of Sample Size

A total sample size of 106 patients is planned for a 1:1 randomization in order to provide 90% power to detect a 50% difference in geometric mean C-peptide ($AUC_{\text{mean } 0-120 \text{ min}}$) during an MMTT at 15 months between the active arm and placebo arm using a two-sided test at the 0.05 significance level. The sample size has been adjusted to allow for 10% loss to follow-up. This is based upon a t-test employing $\ln(X+1)$ normalizing transformation of C-peptide ($AUC_{\text{mean } 0-120 \text{ min}}$) during an MMTT at 15 months and assumed mean and standard deviation estimates, on the transformed scale, of 0.134 and 0.20, respectively¹

It is estimated that there will be a screening failure rate of 16%. To ensure that 106 patients are screened and enrolled approximately 127 patients will be screened.

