13.2.5 Adjustment for Covariates

Change from baseline analyses will be adjusted for baseline and all other analyses will be adjusted for randomization strata (GAD65A level).

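### The two Month 15 C-peptide responder tests leave out baseline C-peptide and name no interval for the treatment difference: valid, but avoidably inefficient

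*Protocol*

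**What the plan says.** Section 13.2.3.2.2 places both responder endpoints in a group that is summarised descriptively, with this test and interval: "p-value from Cochran/Mantel-Haenszel Test stratified for randomization strata (GAD65A level) will be given along with 95% CIs calculated according to the Clopper-Pearson method". Section 13.2.5 gives the general covariate rule: "Change from baseline analyses will be adjusted for baseline and all other analyses will be adjusted for randomization strata (GAD65A level"). A Month 15 proportion is not a change score, so under that rule it receives the stratum and not the baseline value.

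The baseline value exists. Section 7.1.1.4 and Table 2 schedule an MMTT with C-peptide at Visit 2. The primary MMRM in Section 13.2.3.1 includes log-transformed baseline C-peptide AUC. Section 13.2.3.2.2 applies the same model to the change in maximum C-peptide and to the C-peptide values at 30, 60, 90 and 120 minutes.

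On intervals, Section 13.2.2 promises a p-value and a 95% confidence interval with every analysis, without naming an effect measure. Section 13.2.3.2.2 does name between-arm intervals for glycemic variability (a difference) and for severe hypoglycemia episodes (a rate ratio). For the responder endpoints it names only Clopper-Pearson.

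**The concern.** Whether a patient is above 0.2 nmol/L at Month 15 can be expected to depend on how much C-peptide the patient had at entry. A test that ignores this treats predictable variation as noise and loses power. Randomisation is stratified by country and GAD65A level (Section 10.1.1), not by C-peptide, so a chance imbalance in starting C-peptide would also pass straight into the comparison. The same measurement is baseline-adjusted when analysed as a continuous variable and loses that adjustment once dichotomised.

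The second gap concerns reporting. Clopper-Pearson is an exact interval for one proportion. It shows how precisely each arm's rate is known, but gives no interval for the treatment effect that the p-value tests.

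**Working it through.** **Inputs from Section 13.1.** Test: "using a two-sided test at the 0.05 significance level". Target: "90% power to detect a 50% difference in geometric mean C-peptide". Mean and SD "on the transformed scale, of 0.134 and 0.20, respectively". Size: "A total sample size of 106 patients is planned for a 1:1 randomization". Dropout: "The sample size has been adjusted to allow for 10% loss to follow-up".

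**Reproducing the planned size.** Per arm, n = 2(1.960 + 1.282)² × 0.20² / 0.134² = 46.8, so 47. Then 47/0.9 = 52.2, so 53 per arm and 106 in total, as stated. This works only if 0.134 is read as the between-arm difference. Read as a placebo mean with X raised by 50%, the difference is 0.061 and n is 228 per arm. That is a separate matter; here 0.134 is used as the difference. Evaluable patients: 53 × 0.9 = 47.7, about 48 per arm (exact t-test power 0.901 at 48).

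**Power of the responder tests.** The protocol gives no responder rates and no baseline-to-Month-15 correlation (ρ), so both are assumed.
- Model: the Month 15 value is latent normal, shifted by 0.134/0.20 = 0.67 SD (or 75% of that) and dichotomised to give the chosen placebo rate. The two GAD65A strata are equal in size and carry no prognostic effect.
- Size: 48 per arm, 3,000 runs per cell.
- Comparison: CMH by GAD65A against a logistic score test for treatment with stratum and continuous baseline.

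| Placebo v active rate | ρ = 0.3 | ρ = 0.5 | ρ = 0.7 |
|---|---|---|---|
| Full effect, 50% v 75% | 0.72 → 0.75 | 0.72 → 0.80 | 0.72 → 0.86 |
| Full effect, 65% v 85% | 0.66 → 0.68 | 0.65 → 0.71 | 0.65 → 0.81 |
| Full effect, 80% v 94% | 0.50 → 0.52 | not run | not run |
| 75% of effect, 50% v 69% | 0.48 → 0.51 | 0.51 → 0.57 | 0.48 → 0.64 |
| 75% of effect, 65% v 81% | 0.43 → 0.45 | 0.43 → 0.48 | 0.43 → 0.58 |
| 75% of effect, 80% v 91% | 0.33 → 0.36 | 0.34 → 0.39 | 0.34 → 0.45 |

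A further simulation at 60% v 80% gave CMH power of about 58%, rising to 61%, 65% and 75% at ρ = 0.3, 0.5 and 0.7. Together the gains are about 3 points at 0.3, 5 to 8 at 0.5 and 11 to 17 at 0.7, in the same direction in every cell.

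In patients, the equivalent is ((1.96 + z of new power)/(1.96 + z of old power))². For the first row:
- ρ = 0.3: (2.634/2.543)² = 1.07
- ρ = 0.5: (2.802/2.543)² = 1.21
- ρ = 0.7: (3.040/2.543)² = 1.43

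That is about 7%, 21% and 43% more patients.

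**Type I error** (nine null cells; Monte Carlo standard error √(0.05 × 0.95/3000) = 0.004).
- CMH: 0.046 to 0.055.
- Score test: 0.049 to 0.059 (0.052 to 0.061 in the 60% v 80% simulation).
- Likelihood-ratio test: 0.050 to 0.068, highest at a placebo rate of 80%.

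**Intervals.** Take 24/48 against 35/48 as an example. Clopper-Pearson gives 35% to 65% and 58% to 85%. The difference is 22.9 points. Its simple Wald interval is 22.9 ± 1.96 × √(0.500 × 0.500/48 + 0.729 × 0.271/48) = 22.9 ± 18.9, or 4.0 to 41.8 points. The per-arm intervals overlap while the interval for the difference excludes zero, so the first cannot stand in for the second.

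**The case against.** The strongest reply is that CMH stratified on a randomisation factor is a standard, valid test, and that a more efficient alternative is a preference. Validity stands: the simulations put CMH at its nominal level. A reader might infer that the responder p-values are wrong, or that the trial's conclusion is exposed. Neither follows. Both endpoints are outside the four-step sequence in Section 13.2.4, and Section 13.1 makes no power claim for them.

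It is also fair that the continuous forms of these variables are already planned with the baseline-adjusted MMRM, so the trial does not lose the baseline information altogether. That limits the consequence. It does not explain why the dichotomised form should be analysed without it.

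A reader might infer that no confidence interval for the effect will be reported. That is too strong. Section 13.2.2 promises 95% intervals throughout, both arm proportions will be shown, and Section 13.2 leaves details to the SAP. What stands is that the one method named cannot supply the interval for the difference.

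A reader might take Section 13.2.5 as barring baseline adjustment outside change scores. It contains no such exclusion, and it cannot be read as two exclusive classes, since the primary change analysis adjusts for both baseline and stratum. It simply does not assign baseline adjustment here.

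Finally, a reader might extend the point to "Quality adjusted life years (QALYs) based on the EQ-5D-5L questionnaire", arguing that baseline utility forms part of the outcome. The protocol states no QALY formula and no QALY comparison model, and Section 13.2.3.3.3 refers to the EQ-5D-5L User guide. Any weight given to baseline utility would rest on an assumed formula, so the documents do not support that extension.

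**Conclusion.** The point holds as a matter of efficiency and reporting. The named analysis discards a covariate that is already collected and already used in the primary model, and the named interval does not address the treatment effect.

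The reporting gap needs no assumption. The power gain rests on assumed responder rates and correlations, on about 48 evaluable patients per arm, and on reading 0.134 as the between-arm difference. At low correlation the gain is slight. Some of the apparent advantage of a likelihood-ratio test would be inflated size, which is why the figures above use the score test. Even the score test sits marginally above 5% when non-responders are few.

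This is a worthwhile improvement to two lower-tier secondary endpoints and not a condition for the trial's validity.

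**What to change.** In Section 13.2.3.2.2, analyse both C-peptide proportions by logistic regression with treatment, GAD65A stratum and the log baseline value of the same C-peptide measure (maximum or 90-minute, from the Visit 2 MMTT). Take the p-value from the score test, with a Firth-penalised fit pre-specified for the case of few non-responders; avoid the likelihood-ratio test. Report the standardised (marginal) risk difference with its 95% CI. Keep the stratified CMH test as a supportive analysis, and state that Clopper-Pearson intervals describe the per-arm rates. In Section 13.2.5, add that these responder analyses are adjusted for baseline C-peptide as well as stratum.

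The cost is wording and one extra model per endpoint, with no new data. The downside is some model dependence. A score-test p-value and a standardised interval may also disagree at the margin, so the p-value that counts should be named in advance. All of this should be fixed before unblinding, because a covariate chosen afterwards would not be credible.

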- h. The patient will record injection site reactions in the eDiary starting the day after injection and for 7 days following the injection. Injection site reactions reported by patients in the eDiary during day 1-7 following an injection should not be reported as an AE in the eCRF. Any injections site reactions reported after the 1 week recording period will be recorded as AEs in the eCRF.
- i. Patients will record insulin dose in the eDiary for 4 days prior each visit starting from Visit 2. Insulin dose collected at Visit 2 (for the 4 days prior to Visit 2) will be done by the Investigator and recorded in the eCRF.
- j. FGM during 2 weeks post visit for Visits 1, 6 and 7. Patients will be given instructions on when and where to return the device after the testing period. For instruction on how to return the Freestyle Libre Pro sensor, please refer to the Freestyle Libre Pro Worksheet.
- k. The number of self-reported severe hypoglycemia (defined as needing help from others and/or seizures and/or unconsciousness) should be recorded in the eCRF and each event will be recorded separately.
- l. See Procedure for MMTT in the Operations Manual
- m. Only applicable to patients completing their Visit 7 after 01 January 2020.
- n. Patients that have completely withdrawn from the study will be asked to return for a final visit at month 15, in order to achieve as complete as possible follow-up. See section 8.5 for further details.

Table 3 Schedule of Study Events, Extension Study Period

Event	V8 ^g Month 24
DAY	720 (±14)
General Physical Exam ^a	X
Neurological Assessment	X
Concomitant Medication	X
Vital signs (BP)	X
Pubertal Stage, if applicable ^b	X
eDiary use compliance	X
Insulin Dose Collected ^c	X
FreeStyle LibrePro, FGM ^d	X
AEs	X
Urine Pregnancy Test (menarchal females only)	X
Self-reported severe hypoglycemia ^e	X
QoL questionnaire	X
MMTT ^f	X
Blood Sampling for Safety, Genetics, Vitamin D levels and Immunology:	
Hematology	X
Clinical Chemistry	X
GAD65A titer	X
Vitamin D level	X
Covid-19 serological test	X
Other immunological parameters as specified in Section 6.4.2	X
Urine Analysis:	
Microalbuminuria	X
Creatinine	X
Blood Sampling for Diabetes Status:	
Fasting C-peptide	X
MMTT-induced C-peptide^f	X
HbA1c	X
Fasting Glucose	X
MMTT-induced Glucose^f	X

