13.2.3.3 Analysis of Exploratory Endpoint Variables

All data collected at the 24-month follow-up visit (Visit 8) will be regarded as exploratory endpoints and will be presented using summary statistics including data from the Main Study Period where only the patients that participated in the Extension Study Period will be included. The following statistical analyses will be repeated for the whole study period:

- The change in log-transformed C-peptide $AUC_{\text{mean } 0-120 \text{ min}}$ during an MMTT from baseline to Month 24
- Change in HbA1c between baseline and 24 months
- Change in daily exogenous insulin consumption between baseline and 24 months
- Change in Fasting C-peptide between baseline and 24 months.

- Change in glycemic variability/fluctuations (evaluated from data from continuous glucose monitoring FreeStyle LibrePro, FGM) over 14 day period between Screening and 24 months.
- Rate of hypoglycemic events using Poisson regression including randomization strata (GAD65A level)
- Number of patients having at least 1 severe hypoglycemic event using Cochran/Mantel-Haenszel Test stratified for randomization strata (GAD65A level)
- Change in body weight and BMI between baseline and 24 months

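### Poisson regression for hypoglycaemia counts makes no provision for overdispersion, so this rate ratio's interval and nominal p-value may be too optimistic unless events are very rare

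*Protocol*

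**What the plan says.** Protocol Section 13.2.3.2.2 specifies that the number of self-reported severe hypoglycaemia episodes from baseline to month 15 "will be assessed using Poisson regression including randomization strata (GAD65A level) where rate ratios with 95% CI and p-value will be given". Section 13.2.3.3 lists, for the whole study period, "Rate of hypoglycemic events using Poisson regression including randomization strata (GAD65A level"). That second item is worded for hypoglycaemic events in general, not only severe ones, and all 24-month data are declared exploratory.

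Footnote k of Table 2 (Section 7.1) sets how the data arise: the number of severe episodes "should be recorded in the eCRF and each event will be recorded separately". Repeat episodes in one patient therefore all enter the count.

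Two further provisions bear on the weight of the point. Section 13.2.3.2.2 also plans an analysis of "Number of patients having at least 1 severe hypoglycemic event using Cochran/Mantel-Haenszel Test stratified for randomization strata (GAD65A level"). Section 13.2.4 confines hierarchical testing to the primary endpoint and three key secondary endpoints, and hypoglycaemia is not among them.

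The protocol mentions no scale parameter, robust variance, negative binomial model or fallback for either Poisson analysis.

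**The concern.** Poisson regression takes the variance of a patient's count to equal its mean. When patients differ in underlying risk and some have repeated episodes, the variance exceeds the mean. The model-based standard error of the log rate ratio is then too small by the square root of the variance/mean ratio. The interval is too narrow and the p-value too small, so a few patients with repeats in one arm could yield a nominally significant rate ratio on an endpoint that matters to patients.

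This is a remark on a method that the protocol names, with a better one available at almost no cost. It is not a complaint that detail is missing.

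**Working it through.** **Inputs from the protocol.** Section 13.1: "A total sample size of 106 patients is planned for a 1:1 randomization in order to provide 90% power", hence 106/2 = 53 per arm, "using a two-sided test at the 0.05 significance level". Section 13.2.3.2.2: Poisson regression with the GAD65A stratum. The protocol states no operating characteristic for this analysis, so there is no figure to reproduce.

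**Assumptions, because the protocol gives no value.** Mean events per patient m, and variance/mean ratio V. Counts were generated as gamma-Poisson with V = 1 + k·m, where k is the dispersion.

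**Step 1: large-sample size.** The true standard error is √V times the Poisson one, so the real size of a nominal 5% test is 2·(1 − Φ(1.96/√V)).

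| V | √V | 1.96/√V | Size |
|---|---|---|---|
| 1.5 | 1.22 | 1.60 | 11.0% |
| 2 | 1.41 | 1.39 | 16.6% |
| 3 | 1.73 | 1.13 | 25.8% |

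**Step 2: what this does to the interval.** Take m = 0.5, so 53 × 0.5 = 26.5 expected events per arm. Ignoring the stratum, the Poisson standard error is √(2/26.5) = 0.275. For an observed ratio of 1 the interval is exp(±1.96 × 0.275), about 0.58 to 1.71. At V = 2 the standard error should be 0.275 × 1.41 = 0.389, and the interval about 0.47 to 2.14.

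**Step 3: simulated size with 53 per arm.** No treatment effect, two equal strata, Poisson model with treatment and stratum, Wald test, among trials with events in both arms and both strata:

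| m | V = 1 | Overdispersed |
|---|---|---|
| 0.5 | 4.0% | 16.2% (V = 2), 27.4% (V = 3.5) |
| 0.2 | 3.8% | 8.0% (V = 1.4), 14.4% (V = 2), 21.5% (V = 3) |
| 0.1 | 1.6% | 5.4% (V = 1.5), 8.4% (V = 2), 15.8% (V = 3) |
| 0.05 | 0.1% | 1.2% (V = 1.5), 4.3% (V = 2) |

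A further simulation over m = 0.2 to 0.5 gave 9–11% at V = 1.5, 12–16% at V = 2 and 24–25% at V = 3. Taking the two together, the result at V = 3 is about 22–25%.

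At m = 0.05 (106 × 0.05, about 5 events in the whole trial) the Wald test is not inflated up to V = 2, the highest ratio tried there. A likelihood-ratio test on arm totals rejects 21.8% at V = 2, but already 8.7% with no overdispersion, so much of that is sparse data.

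**Step 4: the alternatives.** Negative binomial regression or Pearson scaling held the size to at most about 6% (m = 0.2 to 0.5, V up to 3). In the fuller grid of Step 3, Pearson scaling never exceeded 5.6%. At V = 2 it gave 3.6% (m = 0.2) and 4.9% (m = 0.5). Sandwich standard errors gave 6.4% and 6.1% in those two settings, but 13.2% at V = 11 (m = 0.5).

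**The case against.** The strongest reply is that the protocol does not exclude a dispersion correction. Its sentence does not even name the treatment term, so it is plainly not a full model statement. Section 13.2 leaves details to the SAP, and a Poisson model with scaled or robust errors is still Poisson regression. This stands in part: the SAP could put the matter right without contradicting the protocol. However, Section 13.2.3.2.2 defers specific items to the SAP (log-transformations, further glucose-monitoring analyses) and does not defer this one. As worded, the default reading is the model-based interval.

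Three stronger readings are tempting and are not supported.

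- A reader might infer that the p-value is too small whenever counts are overdispersed. The Wald test is not inflated when events are very rare, and severe hypoglycaemia as defined here (help needed, seizure or unconsciousness) may be rare.
- A reader might infer from footnote k that episodes will cluster in a few patients. It shows only that repeats are counted if they occur.
- A reader might infer that follow-up time is ignored. No offset is named, but a rate ratio may imply one. The 10% planned loss to follow-up makes it worth stating, but its absence is weak evidence of an error.

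The planned stratified test on patients with at least one severe event is a real safeguard, because repeats cannot distort it. It would expose a result driven by one or two patients, though it does not correct the rate ratio's own interval.

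**Conclusion.** The point holds conditionally and is minor. The named model has no provision for overdispersion. If the variance/mean ratio is 1.5 to 3 and the mean is 0.2 to 0.5 events per patient, the false-positive rate of the nominal 5% Wald test is roughly two to five times its stated level. Both quantities are assumptions. The figures are for 53 per arm over the main period and do not carry over directly to the 24-month analysis, which includes only extension participants.

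A reader might take this as a threat to the trial's main conclusion or its controlled error rate. It is not: the 15-month endpoint is an other secondary endpoint outside the hierarchy, and the 24-month one is exploratory. What is at stake is the credibility of one rate ratio's interval and nominal p-value at each time point.

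**What to change.** In Sections 13.2.3.2.2 and 13.2.3.3 (with the matching line in Section 6.4.3), or in the SAP, replace Poisson regression by negative binomial regression with treatment, GAD65A stratum and log follow-up time as offset. If it does not converge, use Poisson regression with Pearson-scaled standard errors. That fallback is preferable to sandwich errors, which are less reliable at high dispersion. Use the same model at 15 and 24 months, and state which test produces the p-value. Keep the stratified test on patients with at least one severe event alongside it.

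The cost is a line of wording at each place. The downside is a wider interval when overdispersion is present.
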